8.4 Communicable Disease Reporting Requirements

Study staff will comply with all applicable local requirements to report communicable diseases identified among study participants to local health authorities. Participants will be made aware of all reporting requirements during the study informed consent process.

8.5 Study Discontinuation

The study may be discontinued at any time by NIAID, NIDA, the HPTN or Gilead Sciences, Inc., other government or regulatory authorities (e.g., OHRP), or site IRBs.

9.0 LABORATORY SPECIMENS AND BIOHAZARD CONTAINMENT

9.1 Local Laboratory Specimens

As described in Section 5, specimens will be processed at the local site laboratories (LL) with tests that include HIV testing (e.g., HIV screening tests, HIV confirmatory tests; HIV RNA tests); hepatitis testing (HBsAg, HBsAb, HBCoreAb, anti-HCV Ab), CBC with differential, chemistry tests (BUN, creatinine, calculated creatinine clearance, hepatic function tests [ALT and AST, total bilirubin], STI tests (syphilis testing following local standards, urine for NAAT for GC/CT, rectal swabs for NAAT for GC/CT [rectal NAAT for GC/CT can also be done at the HPTN Network Lab if this testing is not available at the study site]), urine dipstick for protein and glucose. Specimens will also be collected and processed for Pharmacology testing (plasma, lysed PBMCs, DBS). Urine will be collected to test for substances of abuse.

Additional assessments will be performed for participants who acquire HIV infection during the study (see Appendix 1B), including CD4 cell count, HIV viral load, and HIV genotyping; additional specimens will also be collected for storage and analysis at the HTPN NL in these participants.

Testing will be performed in CLIA certified laboratories and/or CLIA waived locations, as appropriate. Laboratories must demonstrate successful participation in relevant External Quality Assurance (EQA) programs.

Participation in the Immunology Quality Assurance (IQA) and/or Virology Quality Assurance (VQA) programs is preferred, but is not required. Laboratories must demonstrate successful participation in the relevant EQA programs.

Each study site will adhere to standards of good clinical laboratory practice, and local standard operating procedures for specimen management including proper collection, processing, labeling, transport, and storage of specimens to the LL. Specimen collection, testing, and storage at the LL will be documented using the HPTN Laboratory Data Management System (LDMS) as described in the SSP Manual.

9.2 Network Laboratory Specimens

As described in Section 5, specimens will be collected for testing at the HPTN Network Laboratory (NL):

9.2.1 Virology

The HPTN Network Laboratory (NL) will perform testing to determine HIV infection status in selected cases (e.g., indeterminate Western blot, suspected acute HIV infection).

Samples from participants who become HIV-infected during the study will be shipped to the HPTN NL for analysis for research purposes. This analysis may include HIV genotyping, HIV phenotyping, HIV subtyping, minority variants assays, or other tests to characterize HIV viruses and/or the host response to HIV infection. Results from individual participants obtained from this testing will not be returned to study sites or study participants.

9.2.2 Pharmacology

Analysis of ARV drug levels will provide an objective estimate of average adherence over a time period that varies with the matrix assessed. Plasma and lysed PBMC samples will be prepared in the LL and shipped to HPTN NL for Pharmacology studies. Specific information regarding sample preparation will be detailed in the SSP Manual. The levels of TFV and FTC in plasma and FTC-TP and TFV-DP in lysed PBMCs will be monitored at Weeks 8, 26 and 52. The specimens will be analyzed in batches at the end of the study, and will not be used for adherence counseling during this study. These assessments will be performed using assays that are approved and monitored through periodic proficiency testing (where available) by the Clinical Pharmacology Quality Assurance Committee (CPQA).

DBS samples will also be collected for assessment of RBC-associated study drug concentrations. Adherence to study drugs and off-study ARV drug use will also be assessed using a high-throughput multi-drug ARV screening assay.

9.2.3 STI Testing

NAAT of rectal swab specimens for GC/CT will be performed at the HPTN NL if these assays are not available at study sites.

9.2.4 Retrospective analysis of substances of abuse

Stored urine specimens will be tested for the presence of substances of abuse (SOA). This analysis will be performed retrospectively using batched samples. Data from individual study participants will not be returned to study sites or study participants.

9.3 Quality Control and Quality Assurance Procedures

The clinical sites will document that their clinical laboratories are certified under the Continuous Laboratory Improvement Act of 1988 (CLIA) and/or participate in DAIDS-sponsored EQA programs. HPTN NL staff will conduct periodic visits to each site to assess the implementation of on-site laboratory quality control (QC) procedures, including proper maintenance of laboratory testing equipment and use of appropriate reagents. HPTN NL staff will follow up directly with site staff to resolve any QC or quality assurance (QA) problems identified through proficiency testing and/or on-site assessments. Throughout the course of the study, the HPTN NL will select a random sample of stored specimens to test for QA purposes. HPTN NL staff will follow-up directly with site staff to resolve any QA problems identified through this process.

9.3.1 QC for HIV diagnostic testing

The HPTN NL will perform HIV diagnostic testing for QC.

Before performing HIV diagnostic testing, all sites must validate their testing algorithm, and the validation study must be approved by the HPTN NL. Local laboratories will perform testing for HIV diagnosis at Screening, Enrollment and other scheduled visits. Algorithms for HIV diagnostic testing will be provided in the SSP Manual.

The HPTN NL must approve the testing algorithm at each site prior to study activation and/or when a site needs to change a kit or test method. Participants who have any reactive or positive HIV test result at the Screening visit are not eligible for study enrollment, even if subsequent testing indicates that they are not HIV infected. If a participant has a reactive screening test at Enrollment, HIV infection status will be confirmed using local HIV testing guidelines. Participants who have a reactive HIV test result at any other study visit will have further testing performed following procedures in the SSP Manual. In addition, if a participant has signs or symptoms consistent with acute HIV infection, or expresses a concern about recent HIV acquisition, testing will be performed using an HIV RNA test. Regardless of whether HIV RNA testing is used for diagnostic testing, HIV infection must be confirmed in all cases using two independent samples.

9.3.2 QC for HIV RNA monitoring

Quantitative HIV RNA (viral load) testing will be performed at local laboratories to monitor HIV infection in any subject with confirmed HIV infection. Viral load testing will be performed in HIV-infected participants at the visit when HIV infection is confirmed, and at subsequent study visits, as described in Appendix 1B. Note that this is distinct from use of qualitative HIV RNA testing performed to determine HIV infection status (see above). Sites must use a CLIA-certified laboratory that participates in an EQA program; VQA program participation is recommended.

9.3.3 QC for CD4 cell count determination

For participants who become HIV-infected during the study, CD4 cell count testing will be performed at the time when HIV infection is confirmed and at subsequent study visits, as described in Appendix 1B. Sites must use a CLIA-certified laboratory that participates in an EQA program; IQA program participation is recommended.

9.4 Biohazard Containment

As the transmission of HIV and other blood-borne pathogens can occur through contact with contaminated needles, blood and blood products, appropriate blood and secretion precautions will be employed by all personnel in the drawing of blood and shipping and handling of all specimens for this study, as currently recommended by the U.S. CDC. All infectious specimens will be transported in accordance with U.S. regulations [42 Code of Federal Regulations (CFR) 72].

9.5 Sample storage

Selected samples from HIV seroconverters and other participants will be shipped to the HPTN NL. At the discretion of the HPTN NL, samples may be transferred to a DAIDS-approved repository. Other specimens will be stored at study sites and shipped to the HPTN NL upon request.

Study site staff will store all plasma, lysed PBMC, urine, and DBS samples collected in this study until all protocol-related testing has been completed, including QC testing and other testing performed at or coordinated by the HPTN NL. The study site will be informed by the SDMC when shipments to the NL are required and will be instructed which samples to ship. In addition, study participants will be asked to provide written informed consent for their blood and urine specimens to be stored after the end of the study for possible future testing. The specimens of participants who do not consent to long-term storage and additional testing will be destroyed at the end of the study.

10.0 ADMINISTRATIVE PROCEDURES

10.1 Protocol Registration

Prior to implementation of this protocol, and any subsequent full version amendments, each site must have the protocol and the protocol consent form(s) approved, as appropriate, by their local IRB/ethics committee (EC) and any other applicable regulatory entity (RE). Upon receiving final approval, sites will submit all required protocol registration documents to the DAIDS Protocol Registration Office (DAIDS PRO) at the Regulatory Services Center (RSC). The DAIDS PRO will review the submitted protocol registration packet to ensure that all of the required documents have been received.

Site-specific informed consent forms (ICFs) *WILL* be reviewed and approved by the DAIDS PRO and sites will receive an Initial Registration Notification from the DAIDS PRO that indicates successful completion of the protocol registration process. A copy of the Initial Registration Notification should be retained in the site's regulatory files.

10.1.1 Protocol Amendments

Upon receiving final IRB and any other applicable RE approvals for an amendment sites should implement the amendment immediately. Sites are required to submit an amendment registration packet to the DAIDS PRO at the RSC. The DAIDS PRO will review the submitted protocol registration packet to ensure that all the required documents have been received. Site-specific ICF(s) WILL NOT be reviewed and approved by the DAIDS PRO, and sites will receive an Amendment Registration Notification when the DAIDS PRO receives a complete registration packet. A copy of the Amendment Registration Notification should be retained in the site's regulatory files.

For additional information on the protocol registration process and specific documents required for initial and amendment registrations, refer to the current version of the DAIDS Protocol Registration Manual.

10.2 Study Activation

Pending successful protocol registration and submission of all required documents, CORE staff will "activate" the site to begin study operations. Study implementation may not be initiated until a study activation notice is provided to the site.

10.3 Study Coordination

Assignment of all sponsor responsibilities for this study will be specified in a Clinical Trials Agreement executed by DAIDS and Gilead Sciences, Inc. Study implementation will be directed by this protocol as well as the SSP manual. The SSP manual - which will contain reference copies of the *Requirements for Source Documentation in DAIDS Funded and/or Sponsored Clinical Trials* as well as the DAIDS Manual for Expedited Reporting of Adverse Events to DAIDS, Version 2.0, dates January 2010 and the DAIDS Toxicity Tables - will outline procedures for conducting study visits; data and forms processing; AE assessment, management and reporting; dispensing study products and documenting product accountability; and other study operations.

Study CRFs and other study instruments will be developed by the protocol team and HPTN SDMC. Data will be transferred to the HPTN SDMC for data entry, cleaning, reporting and analysis. Quality control reports and queries will be generated and distributed to the study sites on a routine schedule for verification and resolution.

Close coordination between protocol team members will be necessary to track study progress, respond to queries about proper study implementation, and address other issues in a timely manner. Rates of accrual, adherence, follow-up and AE incidence will be monitored closely by the team as well as by the HPTN Study Monitoring Committee. The Protocol Chair, DAIDS Medical Officer, Protocol Biostatistician, SDMC Project Manager and CORE Protocol Specialist will address issues related to study eligibility and AE management and reporting as needed to assure consistent case management, documentation, and information-sharing across sites.

10.4 Study Monitoring

On-site study monitoring will be performed in accordance with DAIDS policies. Study monitors will visit the site to

- Verify compliance with human subjects and other research regulations and guidelines;
- Assess adherence to the study protocol, study-specific procedures manual, and local counseling practices; and
- Confirm the quality and accuracy of information collected at the study site and entered into the study database.

Site investigators will allow study monitors to inspect study facilities and documentation (e.g., ICFs, clinic and laboratory records, other source documents, CRFs), as well as observe the performance of study procedures. Investigators also will allow inspection of all study-related documentation by authorized representatives of the HPTN Operations Center, SDMC, NL, NIAID, Gilead Sciences, Inc., and U.S. government and regulatory authorities. A site-visit log will be maintained at the study site to document all visits.

10.5 Protocol Compliance

The study will be conducted in full compliance with the protocol. The protocol will not be amended without prior written approval by the Protocol Chair and NIAID Medical Officer. All protocol amendments must be submitted to and approved by the relevant IRB(s)/EC(s) and the DAIDS Regulatory Support Center (RSC) prior to implementing the amendment.

10.6 Investigator's Records

The study site investigator will maintain and store in a secure manner, complete, accurate and current study records throughout the study. The investigator will retain all study records for at least three years after submission of the CTU's final Financial Status Report to DAIDS, which is due within 90 days after the end of the CTU's cooperative agreement with DAIDS, unless otherwise specified by DAIDS or the HPTN CORE. Study records include administrative documentation — including protocol registration documents and all reports and correspondence relating to the study — as well as documentation related to each participant screened for and/or enrolled in the study — including informed consent forms, locator forms, CRFs, notations of all contacts with the participant, and all other source documents.

10.7 Use of Information and Publications

Publication of the results of this study will be governed by the HPTN Manual of Operations and policies. Any presentation, abstract or manuscript will be submitted by the Investigator to the HPTN Manuscript Review Committee, DAIDS and Gilead Sciences, Inc. for review prior to submission.

11.0 APPENDIX IA - SCHEDULE OF EVALUATIONS AND PROCEDURES

T T			[-
	Screening (up to Day -45)	Enrollment	Weeks 4 ¹ and 8	Week 13	Quarterly (Weeks 26, 39 and 52)
Administrative and Behavioral Evaluations/Procedures					
Informed Consent	х				X^2
Locator information	х	Х	х	Х	Х
Demographic information	х				
Social harms and AE assessment			Х	Х	Х
Behavioral risk assessment (ACASI)		Х		Х	Х
PrEP Discussion	х	Х	X	X	X
C4 Case Conference		Х		Х	Х
HIV/STI risk reduction counseling	х	Х	х	Х	Х
Self-reported study product adherence assessment			х	Х	Х
Initial PrEP adherence readiness assessment ³		Х			
Study product supply ⁴		Х	х	Х	x ⁵
Autonomy Supportive Adherence Counseling		Х	х	х	x ⁵
PrEP Adherence Self-Regulation Questionnaire		Х	х	Х	x ⁵
Client-Centered Care Coordination (C4)		Х	х	Х	Х
Health Care Climate Questionnaire			х	Х	Х
Care Coordination Measurement Tool (provider administered)		Х	х	х	х
Participant Perception of Coordination Questionnaire (self- administered)				x	х
Care Transition Measure					x ⁶
PrEP Adherence Goal Setting		Х	х	х	x ⁵
Front Line Admin Staff Satisfaction					x ⁶
Offer condoms and other prevention supplies	х	Х	х	х	х
Individual Interview for selected participants					x ⁶
Staff Focus Group (after all participants complete study)					х
Clinical Evaluations/Procedures					
Complete medical history including medications	х				
Interim medical history including concomitant meds		Х	х	Х	х
Symptom-Driven Physical Examination	х	Х		Х	х
Blood collection	х	Х	х	Х	Х
Urine collection	х	Х	Х	Х	Х
Rectal swab collection	х				x ⁷
NM ASSIST	Х				x ⁶
Discharge summary to primary provider if applicable at Week 52 or premature discontinuation					х
Hepatitis vaccination or referral if indicated		x ⁸			x ⁸
STI treatment if applicable: synhilis	x				x ⁷
STI treatment if applicable: gonorrhea and chlamydia	X				x ⁷

Laboratory Evaluations/Procedures					
HIV diagnostic testing ⁹	х	Х	х	Х	Х
Hematology (CBC with differential)	x^{10}				

Renal function tests (BUN, creatinine)	х		x ¹¹	Х	x ¹²
Calculated creatinine clearance	х		x^{11}	Х	x ¹²
Hepatic function tests (ALT/AST, bilirubin)	х				
Hepatitis B status (HbsAg, HbsAb, HbcAb)	х				X^8
Urine dipstick for protein and glucose	х	x ¹³		Х	Х
STI testing: syphilis	х				X^7
STI testing: rectal swab and urine NAAT for gonorrhea and	v				\mathbf{v}^7
chlamydia	Х				Λ
Plasma storage for Pharmacology testing ¹⁴		Х	x ¹⁵		x ¹⁶
Lysed PBMC storage for Pharmacology testing ¹⁴			x ¹⁵		x ¹⁶
DBS storage for possible Pharmacology testing ¹⁴			x ¹⁵		x ¹⁶
Urine storage for substance use testing		х	х	х	х
Plasma storage for QC and Virology testing	х	Х	х	Х	Х

¹Conduct a visit consisting of Week 4 procedures 4 weeks after initiating PrEP, or 4 weeks after a participant re-initiates PrEP.

²Individual Interview Informed Consent for selected participants at Week 52.

³ May occur at any time through Week 48.

⁴ Study drug supply and study drug counseling will begin when and if participants agree to begin PrEP.

⁶ At Week 52 only or on exit from study, if prior to Week 52.

⁷ STI testing (syphilis, rectal swab and urine NAAT) are performed only at Screening and Weeks 26 and 52.

- ⁸ For participants who do not have evidence of HBV immunity at Screening, a course of HBV vaccination will begin at Enrollment and continue until completed (some doses will be given at subsequent study visits). For participants who do not have evidence of HBV immunity at Enrollment, HBV testing should be repeated at the discretion of the site investigator during the study if clinically indicated, if the participant has elevated AST/ALT results, or if the participant expresses a concern about having acquired HBV infection. In addition, for participants who do not have evidence of immunity at Enrollment, decline vaccination, and have not been diagnosed with HBV infection during the study, hepatitis testing (HbsAg, HbsAb, HbcAb) should be repeated at Week 52. If a participant acquires HBV infection during the study, stored samples may tested at the HPTN NL for HBV characterization and other HBV-related studies, including HBV resistance testing; these results will not be reported to study sites or participants.
- ⁹ HIV diagnostic testing must be performed according to the algorithms provided in the SSP Manual. The HPTN NL should be consulted in any case where HIV infection status is unclear, one HIV test is reactive, HIV seroconversion is documented, or acute HIV infection is suspected. Additional assessments are required for participants with confirmed HIV infection (see Appendix 1B). Participants who are confirmed to be HIV-infected according to the SSP Manual will have no further HIV diagnostic testing performed at subsequent study visits.
- ¹⁰ Repeat testing prior to initiating PrEP if participants decide to initiatie PrEP post Enrollment.
- ¹¹ Renal function tests (BUN and creatinine) and creatinine clearance are not performed at Week 8.
- ¹² Renal function tests (BUN and creatinine) and creatinine clearance are only performed at Week 52 for participants who report that they have used PrEP in the previous 60 days.
- ¹³ Repeat dipstick urine testing at enrollment if result from the Screening visit is > trace for either protein or glucose.
- ¹⁴ Plasma and lysed PBMC will be collected for ARV drug testing. Plasma may also be tested using a high-throughput multi-drug ARV drug screen (qualitative testing). DBS will be collected for possible ARV drug testing, using assays that are in development. Plasma and DBS samples will be processed and stored for all participants; testing may be limited to a subset of these samples. Lysed PBMC samples will be processed and stored only for participants who report that they used PrEP within 60 days of sample collection.

¹⁵ Week 8 only.

¹⁶ Weeks 26 and 52 only.

- NOTE 1: If any participant wishes to start or restart PrEP after enrollment, eligibility must be confirmed using all Screening criteria. If assessments performed at the Screening visit occurred more than 45 days earlier, all of these assessments, including laboratory tests, must be repeated (see Section 5).
- NOTE 2: For participants who decide to initiate PrEP at or after Week 48, partnerships will be established as applicable with community partners in order to provide adequate clinical care and follow-up.

⁵ Weeks 26 and 39 only.

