Note: Indication and Usage for Pre-exposure Prophylaxis will be reviewed with participants as part of a comprehensive package of risk reduction services. In general, sites must refer to the CDC interim guidelines for PrEP administration

(http://www.cdc.gov/hiv/prep/pdf/PrEPfactsheet.pdf) and to the guidelines for PrEP Indication (https://www.truvadapreprems.com/#). A manual will be created for all sites to follow when introducing PrEP to participants based on safety and efficacy language found in the ICF under "Study Purpose".

If initiating or on PrEP:

- Assess participant's initial readiness for PrEP adherence (only if initiating)
- Self-reported study product adherence assessment
- Study product supply
- Autonomy supportive adherence counseling
- o PrEP Adherence Self-Regulation Questionnaire (participant self-administered)
- PrEP adherence goal setting
- C4 including:
 - Care Coordination Measurement Tool (recorded by providers)
 - Health Care Climate Questionnaire (participant self-administered)

Clinical Evaluations/ Procedures

- Interim medical history including concomitant medications
- Urine collection
- Blood collection

Laboratory Evaluations/ Procedures

- HIV testing per algorithm in the SSP Manual
- Renal function tests (BUN, creatinine at Week 4 only)
- Calculated creatinine clearance (Week 4 only)
- Plasma storage for Pharmacology testing (Week 8 only)**
- Lysed PBMC storage for Pharmacology testing (Week 8 only)**
- DBS storage for possible Pharmacology testing (Week 8 only)**
- Urine storage for substance use testing

• Plasma storage for QC / Virology testing

*Conduct a visit consisting of Week 4 procedures 4 weeks after initiating PrEP, or 4 weeks after a participant re-initiates PrEP.

**Plasma and DBS samples will be processed and stored for all participants; testing may be limited to a subset of these samples. Lysed PBMC samples will be processed and stored only for participants who report that they used PrEP within 60 days of sample collection.

Note: Any participant who has not taken PrEP in the past 60 days and wishes to start PrEP at this visit must first be confirmed to be eligible according to the Screening Visit parameters.

5.5 Week 13

Administrative and Behavioral Evaluations/ Procedures

- Review and update locator information
- Social Harms and AE Assessment
- Behavioral and Psychosocial Risk Survey (ACASI)
- HIV/STI behavioral counseling (pre- and post-test), including risk-reduction counseling
- PrEP discussion

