- Offer condoms and other prevention supplies

Note: Indication and Usage for Pre-exposure Prophylaxis will be reviewed with participants as part of a comprehensive package of risk reduction services. In general, sites must refer to the CDC interim guidelines for PrEP administration

(http://www.cdc.gov/hiv/prep/pdf/PrEPfactsheet.pdf) and to the guidelines for PrEP Indication (https://www.truvadapreprems.com/#). A manual will be created for all sites to follow when introducing PrEP to participants based on safety and efficacy language found in the ICF under "Study Purpose".

If initiating or on PrEP:

- Assess participant's initial readiness for PrEP adherence (only if initiating)
- Self-reported study product adherence assessment
- Study product supply
- Autonomy supportive adherence counseling
- PrEP Adherence Self-Regulation Questionnaire (participant self-administered)
- PrEP adherence goal setting
- C4 including:
 - C4 Case Conference (by staff preferably prior to the Week 13 visit)
 - Health Care Climate Questionnaire (participant self-administered)
 - Client Perception of Coordination Questionnaire (participant self-administered)
 - Care Coordination Measurement Tool (recorded by providers)

Clinical Evaluations/ Procedures

- Interim medical history including concomitant medications
- Symptom-driven physical exam

- Blood collection
- Urine collection

Laboratory Evaluations/ Procedures

- HIV testing per algorithm in the SSP Manual
- Renal function tests (BUN, creatinine)
- Calculated creatinine clearance
- Urine dipstick for protein and glucose
- Urine storage for substance use testing
- Plasma storage for QC / Virology testing

Note: Any participant who has not taken PrEP in the past 60 days and wishes to start or restart PrEP at this visit must first be confirmed to be eligible according to the Screening Visit parameters. This does not have to be performed at a separate "interim" visit. Screening procedures can be repeated at any scheduled study visit if they needed to confirm eligibility for PrEP administration. All assessments to determine eligibility for PrEP initiation (including laboratory testing) must have been conducted within the previous 45 days.

5.6 Weeks 26, 39 and 52

Administrative and Behavioral Evaluations/ Procedures

- Review and update locator information
- Social Harms and AE Assessment
- Behavioral and Psychosocial Risk Survey (ACASI)
- Qualitative Interview (Week 52 only)
- Adherence goal setting (except Week 52)

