- HIV/STI behavioral counseling (pre- and post-test), including risk-reduction counseling
- PrEP discussion
- Offer condoms and other prevention supplies
- Informed Consent for individual interview (Week 52 only)

Note: Indication and Usage for Pre-exposure Prophylaxis will be reviewed with participants as part of a comprehensive package of risk reduction services. In general, sites must refer to the CDC interim guidelines for PrEP administration

(http://www.cdc.gov/hiv/prep/pdf/PrEPfactsheet.pdf) and to the guidelines for PrEP Indication (https://www.truvadapreprems.com/#). A manual will be created for all sites to follow when introducing PrEP to participants based on safety and efficacy language found in the ICF under "Study Purpose".

If initiating or on PrEP:

- Assess participant's initial readiness for PrEP adherence (only if initiating; initiation not allowed to start after Week 48)
- Self-reported study product adherence assessment
- Study product supply (except Week 52)
- Autonomy supportive adherence counseling (except Week 52)

- PrEP Adherence Self-Regulation Questionnaire (participant self-administered) (except week 52)
- C4 including:
 - C4 Case Conference (commencing discharge/transition planning for weeks 39 and 52)
 - Care Coordination Measurement Tool (recorded by providers)
 - Health Care Climate Questionnaire (participant self-administered)
 - Client Perception of Coordination Questionnaire (participant self-administered)
 - Care Transition Measure (Week 52 only or study exit)
 - Front Line Administrative Staff Satisfaction Survey (week 52 only or study exit)

Clinical Evaluations/Procedures

- Interim medical history including concomitant medications
- Symptom-driven physical exam
- Hepatitis vaccination or referral, if indicated
- Blood collection
- Urine collection
- Rectal swab collection (Weeks 26 and 52 only)
- N MED ASSIST (Week 52 only)
- Submit discharge summary to primary health provider, when applicable
- STI treatment, if indicated (based on testing of samples collected at Weeks 26 and 52)

Laboratory Evaluations/ Procedures

- HIV testing per algorithm in the SSP Manual
- Renal function tests (BUN, creatinine for those on PrEP within the past 60 days)*
- Calculated creatinine clearance (for those on PrEP within the past 60 days)*
- Urine dipstick for protein and glucose
- STI testing: syphilis (Weeks 26 and 52 only)
- STI testing: rectal and urine NAAT for GC and CT (Weeks 26 and 52 only)

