6.7.2 Creatinine Elevations

For creatinine elevations >1.5-fold above baseline creatinine (at screening), serum creatinine will be repeated as soon as possible, preferably within 7 days. Participants who fail to have a confirmed test within two weeks of receiving the initial result should be permanently discontinued from use of the study drug and the PSRT should be notified. FTC/TDF will be held for confirmed creatinine elevations >1.5-fold above baseline until creatinine returns to <1.3-fold above baseline, at which point the participant may be re-challenged with FTC/TDF after consultation with the site investigator. Clinicians may re-test creatinine levels more often (i.e., weekly) should they choose; however, after the initial re-test approximately 7 days later, it is not required per protocol to re-test serum creatinine until the next scheduled study visit. If serum creatinine rises again to >1.5-fold above baseline when drug is restarted, the PSRT must be notified and FTC/TDF should be permanently discontinued and the participant will be monitored as deemed clinically appropriate in consultation with the PSRT until level returns to baseline (screening value) or stabilizes.

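### Appendix IA footnote 12 and Section 5.6 disagree on who has renal function tests at Weeks 26 and 39

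*Protocol*

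**What the plan says.** Section 5.6 is a single procedure list for three visits, headed "5.6 Weeks 26, 39 and 52". Its laboratory items include "Renal function tests (BUN, creatinine for those on PrEP within the past 60 days" and "Calculated creatinine clearance (for those on PrEP within the past 60 days". Neither line carries a week limit, although other lines in the list do, for example "STI testing: syphilis (Weeks 26 and 52 only". The asterisk on the renal lines leads to a note about men who start PrEP at or after Week 48. That note sets no week limit either.

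Appendix IA pools the same visits in one column, "Quarterly (Weeks 26, 39 and 52", and marks both renal rows there with footnote 12. The footnote says that the tests "are only performed at Week 52 for participants who report that they have used PrEP in the previous 60 days".

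Section 6.7.2 sets the creatinine hold and re-challenge rules. After the first repeat test, it says "it is not required per protocol to re-test serum creatinine until the next scheduled study visit".

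**The concern.** The two texts agree on Week 52 and differ at Weeks 26 and 39, so a site cannot tell from the protocol who should have creatinine measured at those visits. If sites resolve this differently, renal ascertainment will differ by site.

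This matters for safety because the rules in Section 6.7.2 act only on creatinine results and lean on the visit schedule for follow-up. It also matters for reporting. Toxicity among men who start PrEP is a secondary objective (Section 2.2), and all creatinine adverse events go on case report forms (Section 6.3).

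**Working it through.** **Side by side.** Who has renal tests at each quarterly visit:

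| Source | Week 26 | Week 39 | Week 52 |
|---|---|---|---|
| Section 5.6 | Recent PrEP users | Recent PrEP users | Recent PrEP users |
| Footnote 12, reading A (Week 52 is the only visit) | Nobody | Nobody | Recent PrEP users |
| Footnote 12, reading B (the condition applies only at Week 52) | Everyone | Everyone | Recent PrEP users |

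Both readings are tenable. For A: footnote 6 restricts other marks in the same column to Week 52 or study exit. For B: the column covers all three visits, and footnote 12 speaks only about Week 52.

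The other week-limiting footnotes in that column match Section 5.6: footnote 5 (Weeks 26 and 39), footnote 6 (Week 52 or exit), and footnotes 7 and 16 (Weeks 26 and 52). Footnote 11 (no renal tests at Week 8) matches Section 5.4. Sites therefore have reason to follow footnote 12 as written.

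**Longest interval between scheduled creatinine results.** The protocol gives no figure for this, so there is none to reproduce. Take a man who starts PrEP in week S and stays on it to Week 52. His scheduled results are:

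- eligibility labs, taken at or before S;
- a result at S+4, because footnote 1 says "Conduct a visit consisting of Week 4 procedures 4 weeks after initiating PrEP", and creatinine is among those procedures;
- Weeks 4 and 13 (Sections 5.4 and 5.5);
- Weeks 26, 39 and 52 under Section 5.6, or Week 52 alone on reading A.

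Under Section 5.6 the fixed visits from Week 13 on are 13 weeks apart (26 − 13, 39 − 26 and 52 − 39 all equal 13), so no interval exceeds 13 weeks.

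On reading A, for S up to 35, the longest interval is 52 − max(13, S + 4):

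| Start week S | Last result before Week 52 | Longest interval |
|---|---|---|
| 9 or earlier | Week 13 | 52 − 13 = 39 weeks |
| 13 | Week 17 | 52 − 17 = 35 weeks |
| 26 | Week 30 | 52 − 30 = 22 weeks |
| 35 | Week 39 | 52 − 39 = 13 weeks |

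From S = 35 onward reading A costs nothing against Section 5.6.

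Eligibility labs may be up to 45 days old, about 45/7 = 6.4 weeks. The interval from those labs to the S+4 visit is then at most 6.4 + 4 = 10.4 weeks. That is below 13, so the maxima do not change.

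For a man who starts at enrollment, the scheduled results after baseline fall from five (Weeks 4, 13, 26, 39 and 52) to three (Weeks 4, 13 and 52).

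On reading B there is no added interval for any user. A man not on PrEP gets up to two sets of renal tests that Section 5.6 does not schedule.

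**The case against.** The mismatch in wording is not in dispute. The case on the other side is about its consequence:

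- **Reading B has real support.** Footnotes 5, 6 and 16 state their week limits directly. Footnote 12 is worded differently and ties a PrEP-use condition to Week 52. On that reading every user is tested as Section 5.6 intends.
- **Other text leans towards Section 5.6.** Section 5.0 describes Appendix I as an overview, Section 7.1 expects renal toxicity to be evaluated during follow-up, and Section 10.3 gives the procedures manual a role in visit conduct. A 39-week gap needs a site to adopt reading A and disregard the plain line in Section 5.6.
- **Section 6.7.2 protects men with a known elevation.** Drug is held until creatinine falls below 1.3 times baseline, so a missing result keeps a man off drug. If he has then taken no PrEP for 60 days, restarting requires the screening assessments again.
- **Other checks remain on reading A.** These are the urine dipstick and adverse event assessment at all three visits, creatinine at the clinician's discretion, and roughly monthly review by the safety review team.

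Much of this stands. It narrows the exposure to first detection of a creatinine rise in an uninterrupted user, on reading A only. It does not make the two texts agree. None of the sections cited is a rule of precedence, and the manual cannot be checked here.

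**Conclusion.** The concern holds. Footnote 12 conflicts with Section 5.6 at Weeks 26 and 39 on either reading, and nothing in the protocol reconciles them.

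The worst case is a 39-week interval without a scheduled creatinine, against at most 13 weeks under Section 5.6. It assumes reading A, a start by Week 9, uninterrupted use to Week 52 and no discretionary test. It is a possible consequence of the wording; no actual loss of testing is shown. Reading B leads only to extra tests in non-users.

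The primary endpoints, the sample size and the confidence interval tables are unaffected. The correction should still be made, because this is a safety schedule for a drug with renal hold rules.

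**What to change.** Reword footnote 12 to follow Section 5.6, for example: *At Weeks 26, 39 and 52, renal function tests and creatinine clearance are done only in participants reporting PrEP use in the previous 60 days.* Check that the procedures manual says the same.

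The cost is a one-line correction or a clarification memo to sites. It requires no tests beyond those Section 5.6 already schedules.
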